7.7.2 Analysis of Secondary Efficacy Endpoints

- ➤ Incidence of aborted lesions, defined as treated HL lesions that do not progress to the vesicular or crust stage. A lesion that returns to normal skin without forming a vesicle or crust will be counted as an aborted lesion. Observation period to determine healing will last up to 14 days. The incidence(events) of aborted lesions will be reported by treatment groups and proportions of subjects with at least one Incidence of Aborted Lesions will be compared between the two treatment groups using the Chi square or Fisher's Exact test for categorical data for both ITT and PP populations. Individual subject data for aborted lesions will be presented in Listing.
- ➤ Incidence of recurrence of HL lesions during the 12-month follow-up period will be reported by treatment groups for FU population. Recurrence is determined by assessment from the investigator and documented using NRS symptom scores and face images using the Science 37 Platform.

The percentage of subjects with at least one recurrence of HL lesions during the 12-month follow-up period will be compared between the two treatment groups using the Chi square or Fisher's Exact test for homogeneity of proportions for categorical data using FU population.

CONFIDENTIAL Page 23 of 31

Private and Confidential Study No 21755 Date: DEC 18, 2023

Individual subject data for recurrence of HL lesions will be presented in Listing.

> Time to recurrence of HL lesions, measured in days from resolution of the cold sore treated in the Treatment phase until appearance of a cold sore during the follow-up period. For subjects who do not recur during the follow-up period, the data will be censored at the time of last follow-up. Time to recurrence of HL lesions will be analyzed similarly to the analysis of primary endpoint using KM method for FU population. Individual subject data Listing for time to recurrence of HL lesions will be presented.

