5.1 Inclusion Criteria

Participants are eligible to be included in the study only if all of the following criteria apply:

Age

1. Males or females, 18 years of age or older inclusive;

Type of Participant and Disease Characteristics

- 2. History of recurrent HL lesions where:
 - a. Recurrence is defined as at least 4 episodes in the preceding 12 months;
 - b. At least half of the episodes should be vesicular in nature;
 - c. At least half of the episodes should be preceded by prodromal symptoms;
 - d. Herpes labialis lesions are characterized by their localization on the cutaneous and/or mucosal surfaces of the lips;
- 3. Willing to avoid, during the treatment phase, the use of anti-inflammatory (not including low-dose (81 mg) aspirin), anti-herpetic, antibiotic and antiviral agents as well as steroids or other natural products that would interfere with the immune system response;
- 4. Female participants of childbearing potential must be using a medically acceptable form of birth control during screening [e.g., hormonal contraceptives (oral, patch, injectable or vaginal ring), implantable device (implantable rod or intrauterine device), or a double barrier], abstinence or in same sex relationship and have a negative pregnancy test at Screening and prior to study drug administration. Female participants of non-childbearing potential must be amenorrheic for at least two years or have undergone surgical sterilization (i.e. tubal ligation/occlusion, hysterectomy and/or bilateral oophorectomy);
- 5. Agreement to abstain from any mechanical disruption of the prodromal area or lesion (i.e. scrubbing, lancing, shaving the area, rubbing with alcohol, application of heat emitting devices used for cold sore treatment, etc.);

Informed Consent and Other

- 6. Capable of giving signed informed consent as described in Section 10.1.4 which includes compliance with the requirements and restrictions listed in the informed consent form (ICF) and in this protocol;
- 7. Ability to understand and follow study-related instructions;
- 8. Be willing and able to participate in all scheduled visits, treatment plan, and trial procedures according to the clinical protocol.

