8.1.1 Screening Phase Day 1 (Visit 1)

Note: Visits stated in the assessment periods and their subsequent tasks/procedures will occur as a virtual visit including the assessment of adverse events. This includes the shipment of supplies to the participant's home required to complete the necessary testing before and after the start of study intervention.

At the Screening visit, the Principal Investigator or appropriate designee will discuss with each participant the nature of the study, its requirements and its restrictions. Written Informed consent will be obtained within the Science 37 Platform prior to performance of any protocol-specific procedures.

Page: 38 of 68

Version 5.0

The Screening Phase will be up to 35 days. The following will be determined during the Screening Visit:

- Assignment of a unique SNR;
- Signed Informed Consent Form (ICF);
- Review inclusion and exclusion criteria;
- Participant demographics;
- Medical history (herpes labialis is based on the participant's self-reported history)
- Medication history of all prescription and over-the-counter drugs (including topicals, herbal products, vitamins and nutritional supplements), use of topical heat or cold, and other products of topical application and investigational drugs, taken within 30 days prior to screening;
- History of drug and alcohol use;
- Sitting blood pressure (BP) and pulse after sitting for at least 5 minutes;
- Self-reported height and weight, (for a Body Mass Index [BMI] calculation);
- Menstrual cycle information;
- Urine pregnancy test (if applicable);
- Urine tests for illicit drugs;
- Distribute urine pregnancy test kits (2 if applicable);
- Discuss the procedure to report adverse events;
- Science 37 Platform training;
- Baseline face image;
- Study intervention kit with dosing instructions (randomized participants only).

The Principal Investigator or his/her designee must review all screening results before proceeding to the Run-in phase of the study. Eligible participants will receive their allotted study intervention kit as per randomization, pregnancy test kits and be trained on how to use the Science 37 Platform, study intervention and pregnancy kits prior to starting the Run-in phase.

Participants will use their own device (e.g., smartphone) provided it is compatible with study requirements.

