8.1.3 Run-in Phase

Randomized participants will start a 6-month Run-in phase during which they will be eligible to start study intervention. The start date for the Run-in phase is defined as the verified date of receipt of undamaged study intervention by the study participant. Participants must develop prodromal symptoms within 6 months of the start of the Run-in phase. Participants will be required to perform weekly "check-ins" within Science 37 Platform during the Run-in phase to verify their willingness to participate and if they have had any adverse events not already recorded. Any participant experiencing prodromal symptoms can immediately start study intervention and proceed to the Treatment/evaluation phase. Participants will be instructed to contact the Science 37 study team within 36 hours of study intervention initiation.

Participants who do not experience any prodromal symptoms after 6 months are withdrawn from the study.

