2.4 Randomization

Subjects will be randomized in a 1:1 ratio to either of the treatment groups (Sitavig or placebo). At Screening, qualified subjects will be assigned a unique number (Randomization Number, [RNR]) in ascending numerical order according to the randomization schedule generated prior to the study by Statistics Department at Bayer.

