3 DATA ANALYSIS CONSIDERATION

3.1 General Data Considerations

The following conventions will be applied to analyses/data presentation:

All dates will be displayed in DDMMMYYYY format.

The statistical analyses will be performed by Quartesian (now a part of Veranex Solutions), using Statistical Analysis System (SAS) Version 9.3 (or higher). All Tables, Figures, and Listings (TFLs) will be produced in landscape format. In general, all data will be listed by the subject, treatment and visit but not limited to above variables. The number of variables presented in each Listing can vary. Please refer to Mock TFLs.

Data will be summarized by treatment wherever appropriate. The total number of subjects in the study group (N) under the stated population will be displayed in the header of summary tables. Unscheduled visit data will be presented in Listings, but not in Tables and Figures.

Data will be summarized using descriptive statistics for continuous variables. Unless otherwise stated, descriptive statistics will include total number of subjects with non-missing value of a variable/parameter (n), mean, Standard Deviation (SD), minimum, median, and maximum. The number of missing observations will also be presented, if there are any, at a particular visit. In case

CONFIDENTIAL Page 14 of 31

Private and Confidential Study No 21755 Date: DEC 18, 2023

of n<2, where n indicates the number of evaluable subjects at a particular time point, only n, minimum and maximum will be displayed.

For categorical variables, data will be summarized using number and percentages. The number (n) indicates the number of subjects with a particular value of a variable or event, which should always be less than or equal to the total number of subjects in the respective treatment group (N). The number and percentage of subjects with missing values for a variable/category/event will also be presented, if there are any, for the resulting visits under the "Missing" category.

Unless otherwise stated, all percentages will be expressed to one decimal place. The number and percentage of subjects will always be presented in the form XX (XX.X). Counts of zero in any category will be presented as "0" and if the percentage in any category to be presented is 100, it will be presented as "100".

All statistical testing will be 2-sided at significance level of 0.05 and no multiplicity adjustment will be made.

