7.2 Demography and Baseline Characteristics

The demographic and baseline characteristics will include age (years), gender, ethnicity, race, height (cm), weight (kg), and BMI (kg/m2) will be summarized by treatment group for ITT Population. Continuous variables will be summarized using descriptive statistics (n, mean, SD, minimum, median and maximum) and for categorical variables, the number and percentage of subjects in each category will be summarized.

Individual subject data listings for demographic and baseline characteristics will be presented.

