7.7 Efficacy Analysis

7.7.1 Analysis of Primary Efficacy Endpoint

The primary efficacy variable is DOE, which will be measured in hours (using the Science 37 Platform), of a single treated HL lesion. Observation period to determine healing will last up to 14 days. DOE is defined in detail in section 4.

DOE will be analyzed using Kaplan-Meier method for treatment groups (Sitavig and Placebo). Median, associated 95% CIs and survival probabilities will be estimated using Kaplan-Meier (KM) Method. DOE curves between the two treatment groups will be compared with a log-rank test and the corresponding hazard ratio (with 95% CI) will be estimated using Cox proportional hazard method.

The analysis of primary efficacy endpoint will be performed on both ITT and PP population, with PP population being the primary efficacy population and ITT population being secondary. Individual subject data for DOE will be presented in Listing.

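### Time to recurrence is compared without adjusting for prior 12-month episode count, which gives up some power if outbreak rates differ between people

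*SAP*

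**What the plan says.** SAP 7.7.2 on time to recurrence: "Time to recurrence of HL lesions will be analyzed similarly to the analysis of primary endpoint using KM method for FU population". The method it points to, in SAP 7.7.1, has the curves "compared with a log-rank test and the corresponding hazard ratio (with 95% CI) will be estimated using Cox proportional hazard method". Neither section names a covariate or a stratum, so the Cox model is read here as treatment-only. Protocol 9.4.3 likewise refers back to the primary-endpoint method. On allocation, SAP 2.4 says "Subjects will be randomized in a 1:1 ratio to either of the treatment groups (Sitavig or placebo" and names no stratification factor; Protocol 6.4 names none either.

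Outbreak history enters through eligibility. Protocol 5.1, criterion 2a: "Recurrence is defined as at least 4 episodes in the preceding 12 months". Criteria 2b and 2c then set minimum fractions of those episodes that were vesicular and preceded by prodrome, and exclusion 2 in Protocol 5.2 sets a maximum fraction that aborted spontaneously. The source is self-report at Screening (Protocol 8.1.1): "Medical history (herpes labialis is based on the participant's self-reported history".

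The baseline table in SAP 7.2 covers "age (years), gender, ethnicity, race, height (cm), weight (kg), and BMI (kg/m2) will be summarized by treatment group for ITT Population". Prior episode frequency is not listed.

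**The concern.** How often a person had outbreaks last year is a natural predictor of how soon the next one comes. The plan uses that history to admit participants and then neither balances, describes nor adjusts for it.

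If personal rates differ, frequent recurrers leave the risk set early in both arms, and faster in the arm with the higher hazard. The hazard ratio from a treatment-only model is then pulled toward 1 and the log-rank test loses power. The effect is strongest when most participants have the event.

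Three features of this design add to the case:

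- Under Protocol 8.1.6 a participant's follow-up ends at the first documented outbreak. Each person gives at most one event, so repeat events cannot supply information on personal rates.
- The Follow-Up population (SAP 6.1) is a subset of ITT fixed after treatment by lesion status. Randomisation does not fully guarantee that outbreak history is balanced there, and the planned tables would not show an imbalance.
- Recurrence accounts for two of the stated secondary objectives, and Protocol 2.2 singles out the earlier trial's recurrence result as notable.

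**Working it through.** **No figure to reproduce.** Sample size is redacted (SAP 2.3), and the documents give no event count, no effect size for recurrence and no spread of outbreak rates. All power figures below rest on assumptions.

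**Inputs from the documents.** Two-sided 0.05 (SAP 3.1: "All statistical testing will be 2-sided at significance level of 0.05 and no multiplicity adjustment will be made"); 1:1 allocation; entry at 4 or more episodes; an outbreak within 6 months of run-in; follow-up to first outbreak or 12 months; censoring at last follow-up.

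**Assumed.** True hazard ratio 0.70; gamma-distributed personal yearly rates; Poisson prior count; exponential outbreak times.

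**Scale.** Schoenfeld events for 80% power at 0.70: 4 × (1.960 + 0.842)² / (ln 0.70)² = 31.4 / 0.1272 ≈ 247.

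**Size of the attenuation.** Treat the spread as gamma with variance v and let Λ be the average cumulative placebo hazard. The marginal hazard ratio is then HR × (1 + vΛ) / (1 + v·HR·Λ). With coefficient of variation 0.57, v = 0.57² = 0.325. At Λ = 1 this gives 0.70 × 1.325 / 1.2275 = 0.756. At Λ = 0 it is 0.70.

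**Simulated power, log-rank against Cox with log(count) only.** Set A has 400 in total, 15% dropout, and recall error of log-SD 0.4 where shown. Set B has 150 per arm and a dropout hazard of 0.15 per year.

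| Spread of personal rates | Log-rank | Cox + log(count) | Change (points) |
|---|---|---|---|
| A: low (CV 0.21), recall error | 89.2% | 89.4% | +0.2 |
| A: moderate (CV 0.43) | 85.7% | 89.8% | +4.1 |
| A: moderate (CV 0.44), recall error | 85.6% | 86.9% | +1.3 |
| A: wide (CV 0.57) | 79.1% | 86.3% | +7.2 |
| A: wide (CV 0.59), recall error | 78.7% | 83.8% | +5.1 |
| B: none | 84.3% | 84.5% | +0.2 |
| B: moderate (gamma shape 4) | 76.6% | 78.7% | +2.1 |
| B: moderate (gamma shape 2) | 74.1% | 78.3% | +4.2 |
| B: wide (gamma shape 1) | 69.0% | 76.4% | +7.4 |
| B: wide (gamma shape 0.7) | 66.1% | 77.3% | +11.2 |

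A third set, with 300 in total, gave -1 to +1 with no or low spread, +4 with moderate spread and +8 to +10 with wide spread.

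Individual wide-spread runs go beyond the 4 to 10 summary at both ends. The highest is the +11.2 at the most extreme shape. The lowest is +2.6, with 200 participants, recall error and follow-up rates at a quarter of the historical rate (43.6% to 46.2%). Simulation error on one power figure at 2,000 trials is at most √(0.25/2000) = 1.1 points.

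**Hazard ratio.** With wide spread, the mean estimate moves from about 0.74 to 0.75 unadjusted to about 0.72 adjusted, against a true 0.70.

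**Type I error.** In set A under the null, log-rank gave 5.0%, 4.6% and 5.6%; Cox with log(count) gave 4.8%, 5.0% and 5.9%. At 2,000 trials the standard error is √(0.05 × 0.95/2000) = 0.49 points, so 5.9% is within simulation error of 5%.

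**Run-in wait as a second covariate.** Used alone it changes power by -1.4 to +2.1 points (set A). Added to the count it changes power by -0.4 to +1.1 (set B).

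**Percentage with a recurrence.** At a constant 4 to 6 episodes a year, 1 − e⁻⁴ = 98.2% to 1 − e⁻⁶ = 99.8% of placebo participants recur within 12 months, and a chi-square test would need 330 to 867 per arm for 80% power at 0.70. Logistic adjustment changes power by -0.1 to +3.7 points with a likelihood-ratio test and by -6.4 to +0.4 with a Wald test. Saturation is the limit here, and adjustment does not cure it.

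**The case against.** The strongest reply is that nothing here is wrong. The SAP follows the protocol's prespecified method, the log-rank test holds its size, randomisation covers chance imbalance, and the unadjusted hazard ratio is a legitimate marginal quantity. All of that stands. A reader might infer that the recurrence result will be biased or invalid, but the documents and the simulations do not support that. The adjusted hazard ratio answers a slightly different, conditional question.

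Four further readings are tempting and go too far:

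- **That the trial holds a numeric count.** Criterion 2a can be met by a yes/no answer. The fractions in 2b, 2c and exclusion 2 need a denominator, which makes a number likely, but no section says it is recorded and the eCRF is not public.
- **That the earlier trial shows wide spread.** Protocol 2.2 reports that more than two thirds of patients had 5 or more episodes a year, all having at least 4. With no spread at all, a Poisson count with mean 4.5 or 5 gives 71% or 76% with 5 or more among those with 4 or more. Gamma shape 1 with mean 4 to 5 gives 80% to 83%. The reported fact fits zero heterogeneity at least as well, so the upper end of the power gain is an assumption.
- **That the run-in wait is a useful second baseline measure.** It can be derived, since "The start date for the Run-in phase is defined as the verified date of receipt of undamaged study intervention by the study participant" and symptom onset is logged. But it is a single waiting time cut off at 6 months, exclusion 26 on prophylactic antivirals does not name the Run-in Phase, and the gain is close to nil.
- **That the percentage comparison needs a logistic model.** The figures above show little gain and a possible loss.

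**Conclusion.** The point holds as a low-cost improvement to one secondary endpoint. The time-to-recurrence comparison leaves out a likely strong predictor that the trial must ask about and very probably holds. The expected gain is about 0 points of power if people's outbreak rates are similar, about 1 to 4 with moderate spread and about 4 to 10 with wide spread. This assumes a hazard ratio of 0.70, 200 to 400 participants and gamma-distributed rates, none of which the public text confirms. Type I error is unaffected. Direction and mechanism are secure; the size is not. Leaving the plan as it stands would not invalidate any result. The point concerns time to recurrence only, and everything depends on the numeric count being available.

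**What to change.** Before database lock and unblinding:

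1. Confirm that the number of episodes in the 12 months before Screening is held in the eCRF or in the Screening source record. If only a yes/no answer exists and no number can be recovered, leave SAP 7.7.2 as it is.
2. If the number is held, make the treatment comparison for time to recurrence a Cox model with treatment and log(prior 12-month episode count). Keep the Kaplan-Meier curves and the unadjusted log-rank test as supportive.
3. Add the count to the SAP 7.2 baseline table and also summarise it by arm for the Follow-Up population.
4. State a simple rule for a missing count, for example the median, and record the change in SAP 7.13.

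Do not add the run-in wait as a covariate, and do not replace the chi-square or Fisher test on the percentage with a logistic model.

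Protocol 9.5 plans an analysis at the end of the Treatment Phase, ahead of the follow-up analysis. The change should therefore be settled before any unblinding for that first analysis.

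The cost is SAP wording and a few lines of code, with no new visits or participants. The hazard ratio becomes conditional on outbreak history and should be labelled so. Retrieving the count from source records would add some data-management work.

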7.7.3 Analysis of Other Efficacy Endpoints

The analysis of other endpoints will be performed on ITT population.

- **Duration of episode (DOE)** will be measured in hours (using the Science 37 Platform), of a single treated HL lesion in subjects who initiate study intervention within 1 hour of onset of prodromal symptoms and subjects who initiated study intervention more than 1 hour after onset of prodromal symptoms. DOE will be analyzed similarly to the analysis of primary efficacy endpoint using KM method. Individual subject data Listing for DOE will be presented.
- Fine to cessation of symptoms, measured in hours from the initiation of first dose of study drug. Cessation of symptoms is defined as the absence of sensations of pain, tingling, or burning at the site of the cold sore. Observation period to determine healing will last up to 14 days. Time to cessation of symptoms will be analyzed similarly to the analysis of primary efficacy endpoint using KM method. Individual subject data listing for Time to cessation of symptoms will be presented.
- ➤ Quality of life score, as measured by the OHIP-14 questionnaire at 3-, 7- and 14-days post-dose will be analysed using Cochran-Mantel-Haenszel (CMH) method with a modified ridit score. The number and percentage of subjects will be summarized for each question/item in OHIP-14 questionnaire by scheduled visits and treatment groups. The actual values of OHIP-14 weighted score for subscale category questions will be summarized by scheduled visits and treatment groups. The post-dose values will be compared between the Sitavig and placebo groups using two sample t-test assuming the normality of data and if the data is non-normal then Wilcoxon Rank-Sum test (also known as the Mann-Whitney U test) will be used. Please refer the Section 9.2 in this SAP for weight factors associated with subscale category questions. Individual subject data listing for OHIP-14 will be presented.
- ➤ Global assessment of treatment efficacy at Day 14 using a 5-point scale (0=none, 1=poor, 2=fair, 3=good, 4=excellent) will be analysed using CMH method with a modified ridit score. The number and percentage of subjects will be summarized for Global assessment of treatment efficacy. Individual subject data listing for Global evaluation will be presented.

CONFIDENTIAL Page 24 of 31

Private and Confidential Study No 21755 Date: DEC 18, 2023

- The change from baseline to post-dose in NRS. The actual and the change from baseline values of NRS score for each symptom/question will be summarized by scheduled visits and treatment groups. The change from baseline to post-dose values will be compared between the Sitavig and placebo groups using two sample t-test assuming the normality of data and if the data is non-normal then Wilcoxon Rank-Sum test (also known as the Mann-Whitney U test) will be used. Individual subject data Listing for NRS scores will be presented.
- The incidence of detachment or swallowing within 6 hours of dosing will be reported by treatment groups. The percentage of subjects with detachment or swallowing within 6 hours of dosing will be compared between the two treatment groups using the Chi square or Fisher's Exact test for homogeneity of proportions for categorical data. Individual subject data Listing for incidence of detachment or swallowing within 6 hours of dosing will be presented.
- ➤ The percentage of subjects who replace the tablet among those with detachment or swallowing within 6 hours of dosing will be analysed using the Chi square or Fisher's Exact test for homogeneity of proportions for categorical data. Individual subject data Listing of subjects who replace the tablet among those with detachment or swallowing within 6 hours of dosing will be presented.

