8.1.4 Treatment/Evaluation Phase (Day 1)

Participants who start to experience prodromal symptoms before the visible appearance of any signs of HL must document the start time of symptoms in Science 37 Platform, complete a pre-dose (immediately before dosing) 0-10 NRS cold sore symptom evaluation (pain, burning sensation, itching and swelling) and a face image. Prior to the start of study intervention, all WOCBP participants MUST perform a urine pregnancy test, and verify that the results are negative (not pregnant), and record in the Science 37 Platform. After verification of a negative pregnancy test result, the participant may self-initiate study intervention.

Any participant who has a positive pregnancy test or is not sure of the results must contact the Science 37 study team immediately. Participants with a verified positive pregnancy test must not self-administer study intervention and will be withdrawn from the study.

Participants must always record pre-dose NRS and a face image irrespective of the start time of prodromal symptoms in the Science 37 Platform. After the completion of all pre-dose procedures, participants will be instructed to self-administer one (1) tablet. Should the buccal tablet adhere to the upper gum correctly, a second dose/tablet is NOT applied. A second tablet in the treatment kit is provided and labeled "BACKUP". The backup tablet should only be used if an issue occurs applying the first tablet (see Section 6.5).

After dosing, participants will complete the 0-10 NRS cold sore symptom evaluation, and face images at 09:00, 14:00 and 19:00 that day within Science 37 Platform. Depending on time of day study intervention is started, some Day 1 assessments and face images may not be collected if the time (minus the 60 minute window) occurs before the time of dosing. If dosing is started after 19:00, then post-dose NRS and face images will be collected starting the next day at 09:00. All post-dose time point assessments (NRS and face images) have an allowable window of ± 60 minutes.

Version 5.0

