9.2 Sample Size Determination

9.3 Analysis Set

For the purposes of analysis, the following analysis sets are defined:

Table 2 - Analysis Populations

| Participant Analysis Set | Description |
|--------------------------|--|
| Safety | All randomized subjects who take at least one dose of IMP. Safety analyses will be conducted on the safety population. |
| Intent To Treat (ITT) | All subjects who are randomized and provide at least one measure of primary efficacy parameters after the 1 st dose of IMP. |
| Per Protocol (PP) | The Per Protocol population will include all subjects in ITT who complete 14-days of evaluations and do not have any major protocol violations. Any exclusion from PP Population will be determined and documented prior to the database lock. |
| | The primary efficacy analysis population will be PP population and ITT Population will be secondary. The same analysis on ITT Population will be repeated for the primary and secondary efficacy endpoints to assess the robustness of the results based on PP Population. |

Version 5.0 Page: 49 of 68

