6 ANALYSIS POPULATION AND TREATMENT GROUPS

6.1 Analysis Population

Screened Population: All subjects who signed the Informed Consent Form.

Safety Population: All randomized subjects who take at least one dose of IMP.

Intent-to-treat (ITT) Population: All subjects who are randomized and provide at least one measure of primary efficacy parameters after the first dose of IMP i.e., if there is at least one non-missing assessment of subject's face image using a 6-point Likert scale after study drug initiation.

PP Population: The Per Protocol population will include all subjects in ITT who complete 14-days of evaluations and do not have any major protocol violations. Any exclusion from PP Population will be determined and documented prior to the database lock.

Follow-Up Population: The Follow Up population will be a subgroup of the ITT population who will continue into the 12 month follow up period and will be defined as patients whose lesions were all treated at the end of the Treatment Phase (of 14 Days) of the trial.

CONFIDENTIAL Page 20 of 31

Private and Confidential Study No 21755 Date: DEC 18, 2023

The primary efficacy analysis population will be PP population and ITT Population will be secondary. The same analysis on ITT Population will be repeated for the primary and secondary efficacy endpoints to assess the robustness of the results based on PP Population.

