7.8 Safety Analysis

The analysis of safety data will include assessments of Adverse Events (AEs) and Vital Signs on the Safety population.

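### Tablet detachment/swallowing and tablet replacement are tabulated only for participants with a scored post-dose face image, although neither endpoint needs one

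*SAP*

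**What the plan says.** SAP 7.7.3 gives one rule for the seven endpoints it covers: "The analysis of other endpoints will be performed on ITT population". Two of the seven concern the tablet itself. For the first, "The percentage of subjects with detachment or swallowing within 6 hours of dosing will be compared between the two treatment groups" by a chi-square or Fisher's exact test. For the second, "The percentage of subjects who replace the tablet among those with detachment or swallowing within 6 hours of dosing will be analysed" with the same tests.

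SAP 6.1 makes ITT membership depend on an image. A randomised participant belongs to it "if there is at least one non-missing assessment of subject's face image using a 6-point Likert scale after study drug initiation". Protocol 9.3 asks only for a post-dose measure of the primary efficacy parameters and does not name the image.

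SAP 6.1 also defines a wider set, the Safety Population: "All randomized subjects who take at least one dose of IMP". Under SAP 7.8 its outcome use is limited: "The analysis of safety data will include assessments of Adverse Events (AEs) and Vital Signs on the Safety population". The summary of participants who took a second tablet (SAP 7.6) is on ITT and PP.

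On the timing of images after evening dosing, Protocol 8.1.4 states: "If dosing is started after 19:00, then post-dose NRS and face images will be collected starting the next day at 09:00". Each post-dose time point has a tolerance of 60 minutes either way.

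**The concern.** Whether a tablet stayed in place for 6 hours is decided by the dosing, not by the lesion. Conditioning its analysis on a later photograph that the independent reader could score selects participants on something that happens after dosing and may be linked to the outcome. Someone whose tablet falls off or is swallowed may lose interest and send no images. That person leaves both the numerator and the denominator of the failure rate, and also leaves the denominator of the replacement rate, which consists of the failures.

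At stake is the descriptive accuracy of the tablet-handling tables. They matter for a product that works by adhesion. They also bear on safety reporting, because SAP 7.6 counts a swallowed tablet followed by the backup as an overdose.

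**Working it through.** The documents give no tablet-failure rate and no expected share of participants without an image, and the sample size text is blacked out. There is therefore no figure of the plan to reproduce. The check compares definitions and timings, then adds an illustration on assumed values.

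**1. What each endpoint needs.** Neither detachment/swallowing nor replacement has an image in its definition. Tablet information has its own route: the reason for a second tablet goes into the eCRF and/or platform (Protocol 6.5), and compliance is checked at Visits 2 and 3 (Protocol 1.3). Tablet status can therefore be known for a person who is outside ITT.

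**2. Can the 6 hours end before an image is due?** After dosing later than 19:00, the first post-dose image is due at 09:00, so the earliest acceptable time is 09:00 − 60 min = 08:00.
- Dosing at 19:00: the window closes at 19:00 + 6 h = 01:00.
- Dosing at 02:00: the window closes at 02:00 + 6 h = 08:00.

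For dosing between 19:00 and 02:00, the whole window is over before a qualifying image can be taken. This is not so at every hour. After dosing at 10:00, an image is due at 14:00 and the window closes at 16:00.

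**3. How easily is someone excluded?** Days 2 to 14 carry 13 × 3 = 39 scheduled images, plus up to 3 on Day 1. One scored image is enough. If each of the 39 were missed independently with probability 0.8, the chance of having none would be 0.8^39 = 0.0002; with probability 0.9 it would be 0.9^39 = 0.016. Occasional misses hardly matter. Exclusion essentially requires stopping almost at once, or sending no image that can be scored.

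**4. Possible shift in the failure rate.** Let m be the share of dosed participants without a scored image, a the failure rate in ITT, and b the rate among those left out. Then:

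rate among all dosed = (1 − m)·a + m·b

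All three values are assumptions. With a = 10%:

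| m | b = 0 | b = 10% | b = 30% | b = 50% | b = 100% |
|---|---|---|---|---|---|
| 1% | 9.9% | 10.0% | 10.2% | 10.4% | 10.9% |
| 3% | 9.7% | 10.0% | 10.6% | 11.2% | 12.7% |
| 5% | 9.5% | 10.0% | 11.0% | 12.0% | 14.5% |
| 10% | 9.0% | 10.0% | 12.0% | 14.0% | 19.0% |

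With b = 40%:
- m = 3%: 0.97 × 10% + 0.03 × 40% = 10.9%
- m = 5%: 0.95 × 10% + 0.05 × 40% = 11.5%

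ITT reports 10.0% in both cases. When b = a there is no bias, and when b < a ITT overstates the rate.

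**5. Replacement endpoint.** On the same b = 40% assumptions, per 1,000 dosed, ITT omits 12 of 97 + 12 = 109 failures (11%) at m = 3%, and 20 of 95 + 20 = 115 (17%) at m = 5%. This endpoint loses a larger share of its own denominator than the incidence does.

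**6. Comparison between arms.** If m and b are equal in the two arms, the difference among all dosed is (1 − m) times the ITT difference. A zero difference stays zero. A spurious difference would need m or b to differ by arm.

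**The case against.** The strongest reply is that a single ITT set for everything under the other efficacy endpoints is prespecified and coherent, and that almost nobody will have none of 39 or more images scored. This stands as a limit on size. It does not make a photograph relevant to whether a tablet detached.

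A second reply is that a person who stops before the first image may also miss Visit 2, so tablet status may be unknown. Moving to the Safety Population could then lower the rate if unknowns were counted as no failure. This stands, and the fix has to deal with it.

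A third is that the exclusions will be visible. SAP 7.1 tabulates Safety and ITT counts by arm, and SAP 7.7.3 plans individual listings of detachment and replacement. SAP 7.5 summarises deviations on the Safety Population, and Protocol 6.5 names a second tablet as a deviation. This stands in part. However, the listings have no stated population, and the deviation table is described only by major or minor category, so none of these gives a tablet-failure rate among all dosed.

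Three stronger readings are tempting, and the documents do not support them:
- **That the symptom, quality-of-life and global analyses lose material data in the same way.** NRS scores are due at the same clock times as the images. OHIP-14 (09:00 on Days 3, 7 and 14) and the global rating (19:00 on Day 14) also fall at image times. Hardly anyone would have these data and no scored image. For time to cessation, a wider set could do harm: SAP section 4 censors everyone without cessation at 14 × 24 = 336 hours, so added early dropouts would count as followed to Day 14.
- **That ITT understates tablet failure.** The direction depends on b relative to a, and the documents give neither.
- **That the comparison between arms is biased.** Protocol 6.2 lists the same excipients for both tablets, and nothing in the documents suggests that exclusion differs by arm.

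**Conclusion.** The point holds for detachment/swallowing and tablet replacement, and for the related second-tablet summary. Both endpoints are restricted by a post-dose condition that has no bearing on them, although a suitable wider population is already defined.

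The effect is probably small. Its size and direction cannot be derived from the documents. The shift of 0.9 to 1.5 percentage points (10.0% against 10.9% to 11.5%) rests wholly on assumed values, and it vanishes if tablet failure is unrelated to having an image. These endpoints are neither primary nor secondary, so the primary and secondary results are unaffected. This is an inexpensive improvement rather than a defect that threatens the trial's conclusions.

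**What to change.** - In SAP 7.7.3, exempt the two tablet endpoints from the ITT rule. Analyse detachment/swallowing and replacement on the Safety Population by randomised arm.
- In SAP 7.6, present the second-tablet summary on the Safety Population as well.
- In all of these, show participants with unknown tablet status as a separate missing category by arm. Do not count them as having had no failure.
- Leave the remaining endpoints in SAP 7.7.3 on ITT.

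The cost is a few lines of SAP text and table shells, using data already collected. The protocol does not stand in the way: Protocol 9.4.4 names no population for these endpoints, and Protocol 9.3 ties PP and ITT only to the primary and secondary efficacy endpoints. The small downside is that some of the added participants may have unknown tablet status, which the missing category makes plain.
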